## **10.4 Secondary Efficacy Analyses**

### **10.4.1 Key Secondary Efficacy Analyses**

The two key secondary efficacy analyses included in the fixed-sequence as described in Section 10.2 are listed below:

1. Efficacy of the 8-week treatment duration compared to the historical 12-week treatment duration will be demonstrated if the lower bound of the two-sided 95% confidence interval for the percentage of HCV GT 1, 2, 3, 4, 5, and 6-infected subjects based on the PP population in the 8-week treatment duration achieving SVR12 is greater than 94%;
2. Efficacy of the 8-week treatment duration compared to the historical 12-week treatment duration will be demonstrated if the lower bound of the two-sided 95% confidence interval for the percentage of HCV GT 1, 2, 3, 4, 5, and 6-infected subjects based on the ITT population in the 8-week treatment duration achieving SVR12 is greater than 93%.

Only if success was demonstrated for both primary efficacy analyses will testing proceed to the two key secondary efficacy analyses in the order listed above. If success has been demonstrated for the first key secondary efficacy analysis of SVR12 based on the PP population in HCV GT 1 - 6-infected subjects, then testing will proceed to the second key secondary efficacy analysis of SVR12 based on the ITT population in HCV GT 1 - 6-infected subjects.

#### 10.4.2 Other Secondary Efficacy Analyses

The other secondary efficacy analyses, which are not included in the fixed sequence, are listed below:

- The percentage of HCV GT3-infected subjects in the PP population who achieve SVR12;
- The percentage of HCV GT3-infected subjects in the ITT population who achieve SVR12;
- The percentage of subjects in the ITT population with on-treatment virologic failure (defined as **On-treatment virologic failure**), and
- The percentage of subjects in the ITT population with post-treatment relapse (defined as **Relapse**12; subjects with reinfection will be summarized separately).

For the analyses of SVR12 among HCV GT3-infected subjects, the number and percentage of subjects achieving SVR12 will be summarized along with a two-sided 95% confidence interval using Wilson's score method.

For the analysis of on-treatment virologic failure and post-treatment relapse, the number and percentage of subjects in the ITT population will be summarized along with a two-sided 95% confidence interval using Wilson's score method.

## 10.5 Sensitivity Analyses

The two-sided 95% confidence interval using Wilson's score method will also be calculated, if applicable, as a sensitivity analysis for the primary and key secondary efficacy analyses of SVR12 based on the PP and ITT populations.

The percentage of subjects in the mITT-GT and mITT-GT-VF populations achieving SVR12, as applicable, will be summarized as well as the corresponding two-sided 95% confidence interval using Wilson score's method and the normal approximation to binomial distribution.

Listings of subjects excluded from the mITT-GT, mITT-GT-VF, and PP populations will be provided, as applicable.

### 10.5.1 Imputation Approaches

In addition to imputing SVR12 as described in Section 6.3, SVR12 will be presented in the ITT population using the following other methods to impute missing HCV RNA values:

- imputing any missing HCV RNA values in the SVR12 window by carrying forward the last non-missing (post-baseline) HCV RNA value prior to the SVR12 window.
- impute as described in Section 6.3 but treat SVR12 non-responders who were categorized as "prematurely discontinued study drug with no on-treatment virologic failure" or "missing follow-up data in the SVR12 window" as successes.

For each of these, the percentage of subjects with SVR12 will be presented along with two-sided 95% Normal and Wilson score confidence intervals.

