**On-Treatment Virologic Failure = Breakthrough or EOT Failure.**

**SVR4** = HCV RNA  $<$  LLOQ in the SVR4 window (4 weeks after the last actual dose of study drug) without any confirmed quantifiable ( $\geq$  LLOQ) post-treatment value before or during that SVR window.

**SVR12** = HCV RNA  $<$  LLOQ in the SVR12 window (12 weeks after the last actual dose of study drug) without any confirmed quantifiable ( $\geq$  LLOQ) post-treatment value before or during that SVR window.

**SVR24** = HCV RNA  $<$  LLOQ in the SVR24 window (24 weeks after the last actual dose of study drug) without any confirmed quantifiable ( $\geq$  LLOQ) post-treatment value before or during that SVR window.

**Relapse12** = confirmed HCV RNA  $\geq$  LLOQ between end of treatment and 12 weeks after last actual dose of study drug (up to and including the SVR12 assessment time point) for a subject with HCV RNA  $<$  LLOQ at Final Treatment Visit who completed treatment and has post treatment HCV RNA data available, excluding reinfection as described below.

**Relapse24** = confirmed HCV RNA  $\geq$  LLOQ during SVR24 window among subjects who achieved SVR12 and have HCV RNA data available during the SVR24 window, excluding reinfection as described below.

**Relapseoverall** = confirmed HCV RNA  $\geq$  LLOQ between end of treatment and up to and including the last HCV RNA measurement collected in the PT Period for a subject with HCV RNA  $<$  LLOQ at Final Treatment Visit who completed treatment and has post treatment HCV RNA data available, excluding reinfection as described below.

Only subjects who have at least one post-treatment HCV RNA value will be included in analyses of relapse. For relapse analyses, the completion of treatment is defined as a study drug duration  $\geq$  52 days for subjects assigned to 8 weeks of treatment. If the regimen is extended to 12 weeks for some subjects, then those subjects will be considered completers if they have a study duration  $\geq$  77 days. If the last available post-treatment value is  $\geq$  LLOQ, then the subject will be considered a relapse (i.e., will not require confirmation).

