### **Reasons for SVR12 Non-Response**

Subjects who do not achieve SVR12 (SVR12 non-responders) will be categorized as having:

1. On-treatment virologic failure (see **On-treatment virologic failure** definition, if a subject meets both definitions of **Breakthrough** and **EOT failure**, he or she will be categorized as **Breakthrough** only);
2. HCV reinfection (see definition described earlier);
3. Relapse12 (see **Relapse12** definition);
4. Prematurely discontinued study drug with no on-treatment virologic failure (defined as any SVR12 non-responder who prematurely discontinued study drug [study drug duration < 52 days for subjects assigned to 8 weeks of treatment, and < 77 days for subjects extended to 12 weeks of treatment] and did not meet the **On-treatment virologic failure** definition);
5. Missing follow-up data in the SVR12 window (defined as any subject who completed study drug without data in the SVR12 window after applying the imputation rules and not meeting the definitions of [1], [2], [3], or [4]);
6. Other (defined as any SVR12 non-responder not meeting the definitions of [1] – [5]).

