## 10.7 Additional Efficacy Analyses

The following additional efficacy analyses will be performed in the ITT population:

- The percentage of subjects with HCV RNA < LLOQ at each post-baseline visit in the Treatment Period (using data as observed);
- The percentage of subjects who achieve SVR4 (HCV RNA < LLOQ 4 weeks after the last actual dose of study drug);
- The percentage of subjects who achieve SVR24 (HCV RNA < LLOQ 24 weeks after the last actual dose of study drug);
- The percentage of subjects who experience post-treatment relapse after achieving SVR12 (**Relapse24**).

In the above analyses for SVR, virologic failure, and relapse, the percentage of subjects with a two-sided 95% Wilson score interval will be summarized. Imputations for missing data will be performed as described in Section 7.0 for analysis of SVR, where a missing response will be imputed as a failure after performing the described imputation. All other endpoints will be presented using data as observed.

A summary of the subjects who completed treatment and relapsed (defined as **Relapseoverall**) will be prepared displaying the number of subjects relapsing overall and by SVR visit window (within the SVR4, SVR12, SVR24 windows or after SVR24 window), including the subject number and the SVR visit window corresponding to the first occurrence of relapse. A similar listing will be prepared for subjects who prematurely discontinued treatment and relapsed after having HCV RNA < LLOQ at their Final Treatment Visit.

A listing of subjects in the ITT population excluded from the relapse denominator (e.g., study drug duration < 52 days for subjects assigned to 8 weeks of treatment) will be provided, as applicable.

The number and percentage of subjects who do not achieve SVR12 will be summarized by reason for non-response (as defined in Section 10.1). A listing of subject numbers and reason for non-response will be prepared. A similar summary and listing will be prepared for subjects who do not achieve SVR24.

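### The second missing-data sensitivity analysis for SVR12 also counts as successes early stoppers whose post-treatment HCV RNA was measured and quantifiable

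*SAP*

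**What the plan says.** SAP 10.5.1 states that, besides the main rule of SAP 6.3 (backward imputation, then local laboratory value, then failure), SVR12 "will be presented in the ITT population using the following other methods to impute missing HCV RNA values". The second method keeps the 6.3 rule but takes SVR12 "non-responders who were categorized as 'prematurely discontinued study drug with no on-treatment virologic failure" and those with "missing follow-up data in the SVR 12 window' as successes". The rate is to be shown with normal and Wilson 95% intervals.

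Both groups come from the reasons for SVR12 non-response in SAP 10.1. Reason 5 requires that no data exist in the SVR12 window after imputation. Reason 4 is any "non-responder who prematurely discontinued study drug [study drug duration < 52 days for subjects assigned to 8 weeks of treatment" (under 77 days if extended to 12 weeks) who did not meet the on-treatment virologic failure definition. It says nothing about whether HCV RNA was measured.

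**The concern.** A sensitivity analysis for missing data may make favourable assumptions about unknown outcomes. It should not reverse known ones. Here the subjects are chosen by reason for non-response, and one of the two reasons can contain subjects with a complete, unfavourable post-treatment record. For them nothing is imputed; an observed failure is overwritten.

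The two methods in 10.5.1 show how far the ITT SVR12 rate depends on missing data. If the favourable one mixes subjects lost to follow-up with subjects known to be viraemic, it overstates how good SVR12 could be had the missing values been favourable. SAP 4.4.2 says the SVR12 results are intended for regulatory submissions.

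**Working it through.** **Step 1. Where does a viraemic early stopper fall?** Following the definitions in SAP 10.1:

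| Subject with < 52 days of drug | Reason for non-response | In the second method of 10.5.1 |
|---|---|---|
| Breakthrough | 1, on-treatment virologic failure | stays a failure |
| Quantifiable at end of treatment, at least 36 days of drug | 1, EOT failure | stays a failure |
| Reinfection | 2 | stays a failure |
| < LLOQ at Final Treatment Visit, then confirmed quantifiable HCV RNA | 4 | **success** |
| < 36 days of drug, still quantifiable at last visit, no breakthrough, quantifiable afterwards | 4 | **success** |
| No HCV RNA in the SVR12 window, none of the above | 4 | success (truly missing) |

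The fourth row cannot be Relapse12: "For relapse analyses, the completion of treatment is defined as a study drug duration" of at least 52 days. The fifth cannot be EOT failure, which needs at least 36 days.

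**Step 2. Does the plan expect such subjects?** Yes. Protocol 5.4.1 follows early stoppers for HCV RNA for 24 weeks. SAP 10.7 plans a listing of "subjects who prematurely discontinued treatment and relapsed after having HCV RNA < LLOQ at their Final Treatment Visit". SAP 10.8 names reason 4 among the groups whose samples are sequenced if HCV RNA reaches 1000 IU/mL after stopping. One person could thus be listed as relapsed, sequenced for resistance, and counted as a success in 10.5.1.

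**Step 3. Size.** The plan gives no figure for this analysis, so none can be reproduced. Inputs:

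- N = 270 (GT1, 2, 4, 5, 6) and 330 (GT1-6), Protocol 8.2.
- Treatment-naïve cirrhotic subjects treated for 12 weeks: 117 + 65 = 182. Three missed SVR12: one stopped early, two had missing data (Protocol 8.2.1, SAP 4.3.1).
- Non-virologic failure in the whole programme: 29/2369 = 1.22%, stated as 1.2%.

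Effect per subject, 100/N: 100/270 = 0.37 points; 100/330 = 0.30 points.

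Possible number at N=330:

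- Closest data: 330 × 1/182 = 1.8, about 2. If all were viraemic: 1.8 × 0.303 = 0.55 points.
- Upper figure: 330 × 29/2369 = 4.0. If all were viraemic early stoppers: 4 × 0.303 = 1.2 points. At N=270 the count is 3.3, so 3 whole subjects give 1.1 points.
- Lower end: 0 subjects, 0 points.

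**Step 4. Illustration at N=330.** Assume the modelled SVR12 rates of 98% (non-GT3) and 92% (GT3) in Protocol 5.6.4.2: 0.02 × 270 + 0.08 × 60 = 10.2, about 10 virologic failures. Add 4 subjects in reasons 4 and 5. The normal lower bound is p − 1.96 × √(p(1 − p)/N).

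| Of the 4, viraemic after stopping | Rate if they stay failures | Normal lower bound | Wilson lower bound |
|---|---|---|---|
| 0 (same as the rule as written) | 320/330 = 97.0% | 95.1% | 94.5% |
| 2 | 318/330 = 96.4% | 94.3% | 93.8% |
| 4 | 316/330 = 95.8% | 93.6% | 93.0% (93.01%) |

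As written, the plan reports the first row in every case. All bounds here exceed 93%. Closer to that figure one subject can matter: at N=270, 13 failures give a normal lower bound of 92.63% and 12 give 93.10%.

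**The case against.** The best defence is that the second method follows a convention used throughout the plan: stopping early without on-treatment failure is non-virologic. The mITT-GT-VF population (SAP 5.1.4) excludes the same group, and SAP 10.3 defends the PP exclusions in similar terms. The method could then be read as the ITT-denominator counterpart of that convention under an imprecise heading, and relabelling it would remove the mismatch. This explains a possible intent, but the section does not state it. A relabelled analysis would also no longer show the effect of missing data, and mITT-GT-VF already gives the virologic-failure view openly, by exclusion.

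Two further points stand largely or wholly. The analysis is descriptive, has no success criterion and lies outside the fixed sequence of SAP 10.2. And the reader is not left blind: SAP 10.7 tabulates and lists reasons for non-response and lists early stoppers who relapsed, and 10.8 lists sequenced subjects. The gaps are narrow. The reason table does not split reason 4 into missing and viraemic; the relapse listing requires HCV RNA < LLOQ at the Final Treatment Visit; and sequencing requires at least 1000 IU/mL.

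A reader might infer that every early stopper is recoded. That is not so: those with breakthrough, EOT failure or reinfection stay failures, and those who reached SVR12 were successes already. A reader might also infer that observed failures enter the trial's main results as cures. They do not: the primary and key secondary ITT analyses count them as failures, and PP excludes anyone with under 52 days of drug.

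**Conclusion.** The point holds within these limits. The second method is described as imputing missing HCV RNA, yet one of its two categories has no missing-data condition, so early stoppers with measured post-treatment viraemia are counted as SVR12 successes in this one sensitivity analysis. No hypothesis test changes.

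The overstatement is 0.37 points per such subject at N=270 and 0.30 at N=330. The number of such subjects is an assumption. The closest historical data suggest about 2 of 330, hence at most about 0.55 points; about 4 of 330, or 1.2 points, is the upper figure and would need every non-virologic failure to be a viraemic early stopper. The true number may be zero. Calling this the favourable end of the missing-data range is an inference from how the method is built; the SAP does not use that label.

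The correction is worth making because the rule gives a wrong result for subjects whom the SAP itself foresees.

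**What to change.** Keep both category restrictions and add a condition on observed data. Proposed text for the second bullet of SAP 10.5.1:

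> Impute as in Section 6.3, but count as successes those SVR12 non-responders in reason categories 4 or 5 of Section 10.1 who (a) have no HCV RNA value in the SVR12 window after imputation, (b) have a last available HCV RNA value that is not ≥ LLOQ, and (c) have no confirmed post-treatment HCV RNA ≥ LLOQ. All other non-responders, including those with on-treatment virologic failure, relapse or reinfection, remain failures.

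The category restriction must stay. A rule based only on absent post-treatment viraemia would turn a subject with breakthrough or EOT failure who is then lost to follow-up into a success; SAP 10.1 foresees a breakthrough value followed by loss to follow-up. Condition (b) fits the existing rule in SAP 10.1 that a last available post-treatment value ≥ LLOQ needs no confirmation to count as relapse. It also keeps as a failure the subject who stops before Day 36 while still quantifiable and is then lost.

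The cost is one sentence in the SAP and one added condition in the program. The sensitivity figure may become slightly less favourable.

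### The second imputation method in SAP 10.5.1 counts as SVR12 successes early discontinuers whose post-treatment viraemia was observed, not missing

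*SAP*

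**What the plan says.** SAP 10.5.1 introduces two alternative presentations of SVR12 in the ITT population, "using the following other methods to impute missing HCV RNA values". The second keeps the Section 6.3 rules but treats two categories of non-responder as successes: those who "prematurely discontinued study drug with no on-treatment virologic failure", and those with missing follow-up in the SVR12 window.

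Both categories are defined in SAP 10.1, under the reasons for SVR12 non-response. The early-discontinuation category covers any SVR12 non-responder with "study drug duration < 52 days for subjects assigned to 8 weeks of treatment" (or below 77 days if extended to 12 weeks) "and did not meet the On-treatment virologic failure definition". The missing-follow-up category, by contrast, is defined by the absence of data in the window after imputation.

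Also in SAP 10.1, Relapse12 is limited to subjects who completed treatment: "For relapse analyses, the completion of treatment is defined as a study drug duration" of at least 52 days for 8-week subjects. SAP 10.7 plans a separate listing of "subjects who prematurely discontinued treatment and relapsed after having HCV RNA" below LLOQ at the final treatment visit. SAP 10.8 has non-responders in this category sequenced when HCV RNA is at least 1000 IU/mL after discontinuation.

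**The concern.** A method for missing values should leave observed outcomes alone. Here the recode is tied to a category label, and the label does not require the outcome to be missing. A subject could appear in the 10.7 listing as relapsed, be sequenced under 10.8 because virus was present, and still be counted as having achieved SVR12 in the 10.5.1 table. That table would then mix two things: what happens if missing outcomes are favourable, and what happens if some observed failures are ignored. A reader who takes the section at its word would attribute the whole difference from the main ITT rate to missing data. SAP 4.4.2 says the SVR12 results are planned for regulatory submissions, so the table should show what its heading says.

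**Working it through.** The plan gives no figure for this rule, so there is nothing to reproduce. The check is a trace through the definitions, followed by the size per subject.

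**Trace.** Take a subject on the 8-week regimen who stops before Day 52, is below LLOQ at the final treatment visit and has confirmed HCV RNA at or above LLOQ afterwards. Protocol 5.1.3 and 5.4.1 follow early discontinuers for 24 weeks with HCV RNA, so such values will be collected.

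1. SVR12: not achieved, because of the confirmed quantifiable post-treatment value (SAP 10.1).
2. On-treatment virologic failure: no, since there was neither breakthrough nor end-of-treatment failure.
3. Reinfection: no, unless a genotype, subtype or clade switch is shown.
4. Relapse12: not possible, because drug duration is below 52 days.
5. Early discontinuation without on-treatment failure: yes.
6. SAP 10.5.1, second method: recoded as a success.

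A second route leads to the same place. End-of-treatment failure requires at least 36 days of drug, so a subject who stops earlier with quantifiable virus and no breakthrough also passes to step 5.

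An early discontinuer with an in-window value below LLOQ and no confirmed post-treatment viraemia is already a responder and never enters the category. It therefore consists essentially of subjects whose SVR12 value is missing and subjects whose viraemia was observed. Only the first group needs imputation.

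**Size per subject.** Inputs: N = 270 non-GT3 subjects and an assumed ITT SVR12 rate of 97% (Protocol 8.2 and the SAP sample-size section); a non-virologic failure rate of about 1%, with 29/2369 = 1.2% observed in the registrational programme (SAP 4.3.1).

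- Expected ITT failures: 270 × 0.03 = 8.1.
- Expected non-virologic failures: 270 × 0.01 = 2.7, or 270 × 29/2369 = 3.3; roughly 3.
- Change in the rate per recoded subject: 1/270 = 0.37 points. For three: 3/270 = 1.11 points.
- Normal lower bound: p − 1.96 × √(p(1 − p)/n). The Wilson bound is shown beside it, since SAP 10.5.1 reports both.

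| Failures of 270 | Rate (%) | Normal lower bound (%) | Wilson lower bound (%) |
|---|---|---|---|
| 8 | 97.04 | 95.01 | 94.26 |
| 7 (one recoded) | 97.41 | 95.51 | 94.75 |
| 5 (three recoded) | 98.15 | 96.54 | 95.74 |

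One recoded subject moves the lower bound by 95.51 − 95.01 = 0.50 points (Normal) or 94.75 − 94.26 = 0.49 points (Wilson).

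**The case against.** The best defence is that the rule is a deliberate best case. The plan already treats non-virologic failure as uninformative about duration: the PP population drops subjects with less than 52 days of drug, and mITT-GT-VF drops everyone who failed for non-virologic reasons. On this view only the missing-values label is loose. That explains how the rule may have arisen but does not rescue it. Those populations leave such subjects out; neither counts a viraemic subject as cured. A best case for missing outcomes still has to keep observed failures.

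It is also fair to say that the recoding could be undone by a careful reader, because SAP 10.7 lists every SVR12 non-responder with the reason and separately lists early discontinuers who relapsed after suppression.

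Several stronger readings are tempting but not supported:

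- *Every early discontinuer becomes a success.* No. Those classed as reinfection are counted only there, and those meeting breakthrough or end-of-treatment failure are on-treatment failures. Both groups stay failures.
- *The rule could turn a failed trial into a passed one.* With 13 failures of 270 the Normal bound is 92.63%, and with 12 it is 93.10%, so one subject can move the displayed interval across 93%. But the SAP attaches no success criterion to this display. The fixed sequence uses the Section 6.3 rule, under which missing counts as failure.
- *The result is no longer an upper bound.* It still is one, only looser than it need be, since recoding extra subjects can only raise the rate. The SAP does not call it a bound in any case.
- *The first method has the same defect.* It fills gaps by "carrying forward the last non-missing (post-baseline) HCV RNA value prior to the" SVR12 window and overwrites no observed failure. Whether on-treatment values should be eligible is a matter of preference about carry-forward.

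**Conclusion.** The point holds as a defect in one sensitivity analysis. Followed literally, the second method in SAP 10.5.1 replaces observed post-treatment viraemia with success for early discontinuers who are neither on-treatment failures nor reinfections, and nothing elsewhere in the SAP corrects this. The primary and key secondary analyses are untouched.

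The size is 0.37 points on the ITT rate and about 0.5 points on the lower bound per subject at N = 270. How many subjects are involved cannot be derived from the documents. The 1% to 1.2% rate covers all non-virologic failures, including missing follow-up, for which recoding is legitimate. Among the 182 historical treatment-naïve cirrhotic subjects (117 + 65), three did not achieve SVR12: two had missing data and one stopped early, and that subject's post-treatment HCV RNA is not reported. The effect on the rate therefore ranges from zero to about 1 point; the upper end assumes that all of the roughly three expected non-virologic failures are viraemic early discontinuers.

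**What to change.** In SAP 10.5.1, second bullet, recode as successes only those non-responders in the two named categories who meet both conditions:

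- the SVR12-window value is still missing after the Section 6.3 imputation; and
- there is no confirmed post-treatment HCV RNA at or above LLOQ, and the last available post-treatment value is not at or above LLOQ.

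The second condition borrows the relapse rule in SAP 10.1, so a single unconfirmed value later followed by one below LLOQ does not bar a subject from recoding. All early discontinuers with observed viraemia under this rule stay failures. The missing-follow-up category should hardly be affected, because it already requires missing data and excludes Relapse12.

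The cost is a sentence of SAP text and one programming condition, with no new data. The sensitivity estimate may come out slightly lower.
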